- The investigators will attempt to contact the participant and reschedule the missed visit planned for Post-op days 10-14 and counsel the participant on the importance of maintaining the assigned visit schedule and ascertain if the participant wishes to and/or should continue in the study.
- Before a participant is deemed lost to follow-up, the investigator or designee will make every effort to regain contact with the participant

(where possible, 3 telephone calls and, if necessary, a certified letter to the participant's last known mailing address or local equivalent methods).

These contact attempts will be documented in the participant's medical record or study file. After 3 attempted phone calls spanning two postoperative days the patient will be deemed lost to follow-up.

- Should a participant be unreachable for one day of the study follow-up this will not be deemed a loss to follow-up, however this occurrence will be documented in the data and accounted for in the analysis phase of the study.

Should the participant continue to be unreachable, he or she will be considered to have withdrawn from the study with a primary reason of lost to follow-up.

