Historically, other methods were used to combat post-operative pain. Buchko et al looked at intra-articular analgesia after arthroscopic ACL reconstruction and found an increased rate of chondrolysis, which was similar to other studies that looked at its use in the shoulder joint (11). Use of peripheral nerve blockade is not new practice and has been described throughout the literature. Manickam et al showed 100% success rate and full blockade after twenty minutes with use of the adductor canal block (12). The safety and efficacy of the Continuous Peripheral Nerve Block (CPNB) has been thoroughly investigated. Carvhalo et al found that the addition of a peripheral catheter added only 10 minutes to procedural time versus single shot peripheral nerve block (14). In a group of 35 trauma patients it was found that despite continuous peripheral nerve infusion, serum levels of Ropivacaine were well below toxic levels (15). A review article by Nicolotti et al found that the incidence of positive cultures of placed catheters varied widely from 6%-57%, but the actual incidence of positive cultures resulting in clinical infection was 0%-3.2% (13). The large discrepancy between the two values was found to be likely due to inadequate skin preparation and improper technique with removal.

Some studies have shown the efficacy of CPNB use and concluded with positive results. A multicenter prospective study of use of CPNBs found high quality postoperative pain reduction along with low rates of neurologic or infectious complications (1) and according to Enneking et al. CPNBs have been shown to improve patient satisfaction and improve rehabilitation compared to IV narcotics after orthopedic surgery for both upper and lower extremity (3). A more recent study prospectively looked at CPNB vs placebo (Normal Saline) performed in the upper extremity and found that there was a statistically significant reduction in pain, opioid use, sleep disturbances and increase in patient satisfaction scores (4). A large meta analysis by Richman et al looked at the efficacy of CPNBs and found statistically significant reduction in opioid use, pain up to 72 hours postoperative and decrease in episodes of nausea and vomiting (5) with use versus opioid analgesia.

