In the lower extremity two main methods of block are employed, femoral nerve block (FNB) or adductor canal block (ACB). The use of FNB in ACL reconstruction, as shown by Mulroy et al, was found to have superior efficacy in pain control and reduction in opioid consumption when testing single shot FNB vs sham (9). One complication of FNB is quadricep muscle weakness, which Jaeger et al. demonstrated as a 49% reduction from baseline while ACB reduced strength 8% from baseline (10). Kwofie et al found that with ACB vs FNB that there was a statistically significant preservation in balance and strength in ACB compared to FNB (8). These studies show the advantages of ACB to anesthetize surgical sites without compromising quadriceps strength and balance. Abdallah et al showed that using ACB versus FNB reduced quadriceps weakness with similar functional outcomes and pain reduction in ACL reconstruction (7). The superiority of

continuous catheter delivery over single injection in regards to pain and reduction and opioid use have not been shown in the literature. To our knowledge there are no randomized controlled trials that compare single injection versus CPNB in the adductor canal following ACL reconstruction. In this study we look to compare these two methods of analgesia after ACL reconstruction examining the effects on pain control, opioid use, and satisfaction scores.

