11. RESEARCH PROCEDURES

- *Include a detailed description of all procedures to be performed on the research subject and the schedule for each procedure.*
- *Include any screening procedures for eligibility and/or baseline diagnostic tests*
- *Include procedures being performed to monitor subjects for safety or minimize risks*
- *Include information about drug washout periods*
- *If drugs or biologics are being administered provide information on dosing and route of administration*
- *Clearly indicate which procedures are only being conducted for research purposes.*
- *If any specimens will be used for this research, explain whether they are being collected specifically for research purposes.*
- *Describe any source records that will be used to collect data about subjects*
- *Indicate the data to be collected, including long term follow-up*

Screening evaluation will occur during the preoperative visit prior to surgery which generally occurs within 28 days prior to surgery. No separate screening is indicated in this study.

Patients will be asked to participate in the study if they are having ACL Reconstruction surgery with one of the orthopedic surgeons who is participating in the study. They will be informed and consented in the office or in the preoperative holding area prior to surgery.

Patients undergo ACL reconstruction at either Plainview, Franklin, Huntington, Long Island Jewish, or North Shore University Hospital.

Any medical condition that is present at the time that the participant is screened will be considered as baseline and not reported as an adverse event (AE). However,

if the study participant's condition deteriorates at any time during the study, it will be recorded as an AE.

Changes in the severity of an AE will be documented to allow an assessment of the duration of the event at each level of severity to be performed. AEs characterized as intermittent require documentation of onset and duration of each episode.

We will record all reportable events with start dates occurring any time after informed consent is obtained until 7 (for non-serious AEs) or 30 days (for SAEs) after the last day of study participation. At each study visit/call, we will inquire about the occurrence of AE/SAEs since the last visit/survey/call. Events will be followed for outcome information until resolution or stabilization.

[figure not shown]
Study procedures and evaluations

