- All patients who are enrolled in this study will have been evaluated and determined to be a candidate for ACL reconstruction surgery. The indications for surgery, determination of need for surgery and physical examination determining this need are independent from the interventions and outcomes being assessed by this study.
- **Efficacy Assessment plan-** All patients will be sent surveys through REDCAP, which is a secure patient secure electronic data capture software on postoperative days 1,2,3,4, 7 and 14. And be assessed in person at the post-operative visit which usually falls between post op day 10-14 depending on weekend and convenience. They will be surveyed for primary and secondary outcomes . Primary outcome will be assessed using visual analog scale 0-10. Secondary outcomes; Opiate consumption, Sleep quality, disturbances in sleep, global health assessment through the SF-12, and knee function through IKDC pre operatively and POD 14. The patient will also be contacted via telephone on post-operative day 1, 2, 3, 4 and 7 to assess for adverse events.
- Screening evaluation will occur during the preoperative visit prior to surgery which generally occurs within 28 days prior to surgery. No separate screening is indicated in this study.
- Procedure for administering study intervention and follow-up procedures. The participant will be seen in the preoperative holding suite prior to surgery to ensure that the patient is still willing to undergo randomization for the study. The patient will then undergo randomization by a computer-based software and the anesthesiologist will be informed of the plan. The participant will undergo anesthesia at the discretion of the anesthesiologist per routine given the participant's clinical baseline. The participant will undergo ACL reconstruction based on the standard of care treatment. Following surgery but prior to leaving the operating room the anesthesiologist will place the adductor canal block and the catheter based on the participant's randomization under ultrasound guidance to ensure proper placement of the block. The participant will then undergo routine

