Outcomes measured on post-operative days 1,2,3,4,7, and at the post-operative follow-up visit.

- Quality of Sleep
 - Trouble falling asleep due to pain (yes,no)
 - Wake due to pain (yes,no)

Outcomes measured at post-operative follow-up visit

- Satisfaction with surgery, on a scale of 0 to 10, where 0 represents extremely dissatisfied and 10 extremely satisfied
- Adverse events: Adverse events will be assessed at each visit. At the end of the study, each subject will be categorized as having had one or more adverse events, or not having had any adverse events.
- Serious Adverse events: Serious adverse events will be assessed at each visit and via telephone on post-operative day 1, 2, 3, 4 and 7. At the end of the study each subject will be categorized as having had one or more serious adverse events, or not having had any serious adverse events.

Statistical Methods:

Primary Outcomes:

For each outcome, repeated measures analysis of variance (RMANOVA), where post-operative pain control method (bolus block, continuous catheter) is the between subjects effect and post-operative day is the within subjects effect will be used to examine the association between pain control method and that outcome. Site (stratification variable) will be included as a covariate in each model. The interaction of post-operative control method and day will be included in the model. If the interaction is significant, then pairwise comparisons of pain control method at each day will be carried out within the RMANOVA model. If the usual assumptions required for the ANOVA model are not met, then a suitable transformation, or an appropriate non-parametric method will be used.

Secondary Outcomes:

For binary outcomes measured on days 1,2,3,4,7 and 10:

For each outcome, a generalized linear mixed model (GLMM) for binary clustered (i.e., hierarchical) data will be used to examine the association between pain control method and that outcome. GLMM will be used to account for the hierarchical structure of the data, (namely, multiple days within a subject). Site (stratification variable) will be included as a covariate in each model.

For binary outcomes measured on day 10 only:

For each outcome, logistic regression will be used to examine the association between pain control method and that outcome. Site (stratification variable) will be included as a covariate in each model.

For satisfaction with surgery:

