16. WITHDRAWAL OF SUBJECTS

- *Describe anticipated circumstances under which subjects will be withdrawn from the research without their consent*
- *Describe procedures for orderly termination*
- *Describe procedures that will be followed when subjects withdraw from the research, including partial withdrawal from procedures with continued data collection.*

Participants may withdraw voluntarily from the study at any given time with no reason as is outlined in the informed consent for participation in the study. Any participant who withdraws from a study arm will still be contacted for follow-up assessments as outlined within this protocol unless the participant elects to forgo follow-up contact with the study assessors. This will include the surveys for outcome assessment, phone calls made on the subsequent postoperative days and the office visit following surgery.

Discontinuation from the continuous administration of local anesthetic prior to completion of the medications' dosing will not be deemed a withdrawal from the study but rather a discontinuation of treatment and the participant will continue to be followed up with for assessment of study outcomes with notation of the discontinuation of treatment within the database and the reason for discontinuation documented.

All participants who discontinue intervention will be followed in order to assess for potential adverse events, serious adverse events and any unanticipated problems pertaining to the use or administration of the study medications.

Adverse events include but are not limited to block failure, allergy to local anesthetic, persistent pain at injection/catheter site, local skin irritation at catheter site, pump/device failure.

Should a participant experience any of the serious adverse events listed in the next section, this participant will immediately be halted from their study intervention. These patients will be recommended to seek immediate care for assessment of their serious adverse event to best ensure patient safety. Should a patient experience an adverse event or unanticipated event, the study investigator who is contacted will determine if the participant's event meets criteria for discontinuation of treatment.

ADVERSE EFFECTS OF TREATMENT

Risks associated with single shot adductor canal block

1. Peripheral Nerve Injury

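### Adverse events are asked about at every contact, but the text shows no targeted item for nausea or vomiting, knee giving way or falls, and the only planned harm comparison is any event versus none

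*Combined protocol and SAP*

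**What the plan says.** **How events are collected.** Section 11 states: "At each study visit/call, we will inquire about the occurrence of AE/SAEs since the last visit/survey/call". It adds: "The patient will also be contacted via telephone on post-operative day 1, 2, 3, 4 and 7 to assess for adverse events". There is also an office visit at postoperative day 10-14. The wording of the question is not given, and no symptom checklist appears.

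**What counts as an event.** Section 16 opens its list with "Adverse events include but are not limited to block failure, allergy to local anesthetic, persistent pain at injection/catheter site" and continues with skin irritation at the catheter site and failure of the pump or device. The risk lists in Sections 16 and 17 add nerve injury, systemic toxicity, infection and catheter dislodgement.

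**What is analysed.** Under Section 12, "each subject will be categorized as having had one or more adverse events, or not having had any adverse events". Serious adverse events get the same ever/never treatment. Both are compared by logistic regression with site as a covariate. The survey row of the Section 11 schedule lists pain, sleep disturbance and opioid consumption, with no harm item.

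**What the background raises.** Section 3 reports a 49% loss of quadriceps strength with femoral block, whereas "ACB reduced strength 8% from baseline", with balance also better preserved. It cites a "decrease in episodes of nausea and vomiting" with continuous blocks compared with opioid analgesia.

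**The concern.** The trial expects the catheter to reduce pain and opioid use. Two natural follow-up questions are whether lower opioid use brings less nausea, and whether two to three days of block, largely at home, is accompanied by more knee giving way or falls. The plan specifies no direct measurement of either.

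A general question leaves it to the patient and the caller to decide whether nausea after surgery or a buckling knee is an adverse event. Neither is blinded, so that judgement could differ between arms. Catheter patients also receive pump instruction and troubleshooting contact, and may return for removal, which gives extra occasions for reporting. Unequal reporting is therefore possible, though not shown.

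Whatever is recorded then enters a single ever/never variable in which a benefit on one symptom can be offset by device problems that the other arm cannot have.

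**Working it through.** **1. The plan's own figure.** The only sample-size figure concerns pain: difference 2, SD 2.5, two-sided alpha 0.01, 80% power (Section 12). The normal approximation gives n = 2 × (2.5/2)² × (2.576 + 0.842)² ≈ 36.5, so 37 per arm. The exact two-sample t-test gives 38.2, so 39 per arm, with 81.0% power at 39. The stated 39 reproduces. No calculation is given for harms.

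**2. Is the gap filled elsewhere in the text?**
- Surveys (Section 11 schedule): pain, sleep and opioid use only.
- Section 12 secondary outcomes: sleep, satisfaction, any adverse event, any serious adverse event.
- Risk lists (Sections 16 and 17): nausea, vomiting, giving way and falls are not named.
- Nerve examination (in the single-shot risk list): done once the patient is awake, and only deficits greater than the block would explain are followed. Block-related weakness at home is outside it.
- IKDC and SF-12: before surgery and at day 14, so neither is collected during the 48-72 hour infusion.
- Section 12 mentions the telephone calls only for serious events, whereas Sections 6 and 11 use them for all adverse events. The passages should be reconciled so that early non-serious events clearly count.

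**3. Effect of incomplete capture (assumed rates).** Power is Φ[(|p1 − p2| − 1.96·s0)/s1], with s0 = √(2p̄(1 − p̄)/39) and s1 = √((p1(1 − p1) + p2(1 − p2))/39), at two-sided 5%.
- 40% vs 20%, all captured: s0 = 0.1038, s1 = 0.1013; (0.20 − 0.2034)/0.1013 = −0.03; power 48.7%. The 95% CI half-width for the risk difference is 1.96 × 0.1013, about 20 points.
- Half captured in both arms, 20% vs 10%: s0 = 0.0809, s1 = 0.0801; (0.10 − 0.1585)/0.0801 = −0.73; power 23.3%.
- Other assumed pairs, fully captured: 5% vs 15% gives 31%, and 10% vs 30% gives 60%.
- Unequal capture with no true difference: 30% in both arms, with 50% and 80% recorded, appears as 15% vs 24%.

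**4. Rare events.** With 0 events in 39 patients, the one-sided 95% upper limit is 1 − 0.05^(1/39) = 7.4%. If only half of true events were recorded, the limit on the true rate would be 7.4%/0.5 = 14.8%.

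**5. Dilution in the any-event variable (assumed rates, independence).** Suppose nausea truly falls from 40% to 20%, and catheter-only events affect 10% of that arm, borrowing the top of the plan's 0-10% range for local inflammation. Any-event is then 40% vs 1 − 0.80 × 0.90 = 28%, with power about 20%. At 20% catheter-only events it is 40% vs 1 − 0.80 × 0.80 = 36%, and a halving of nausea is nearly invisible.

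**The case against.** A reader might infer that the harm comparison rests on volunteered reports and that the plan recognises only block, allergy and device problems. The documents support neither. Section 11 commits staff to ask at each contact, on the same call schedule in both arms. The Section 16 list is expressly open-ended, it names site pain and skin irritation, and the same section covers nerve injury, toxicity and infection. The accurate description is solicited but untargeted questioning.

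The background should not be overread either. It ties marked weakness to femoral block, which neither arm receives, and uses the contrast to support the adductor canal approach. The nausea result compares continuous block with opioid analgesia, not with a single-shot block. Falls do not appear in the background text; fall risk occurs only in a reference title. No stated objective concerns these symptoms.

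Three further points have weight:
- Section 15 refers to an attached data and safety monitoring form, and the case report forms are not in the text. A checklist there cannot be excluded.
- Section 11 requires severity changes, and onset and duration of intermittent events, to be documented, so recorded events could still be tabulated by type.
- The rates above are assumed. The 15% vs 24% example follows directly from assuming unequal reporting, and even full capture gives only about 49% power in the 40% vs 20% case.

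All of this stands and narrows the point. It does not supply a targeted question in the reviewed text. Tabulating by type helps only for events that were recorded, and symptoms missed during the infusion cannot be recovered reliably at day 14.

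**Conclusion.** The point holds as a worthwhile, inexpensive improvement. It is not a flaw that invalidates a planned analysis. The visible text has no specific item for nausea or vomiting, giving way or falls during the infusion window. It relies on a general question in an unblinded trial and compares harms only through a composite containing catheter-only events.

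The size cannot be fixed from the documents, which give no rates for these symptoms. Under an assumed 40% vs 20%, recording half the cases lowers power from about 49% to 23%. Under the dilution assumptions, the any-event comparison has about 20% power or less. Because power is limited even with complete capture, the added items should be treated as descriptive. The conclusion would be softened if the monitoring form or case report forms already contain a symptom checklist.

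**What to change.** - Add three closed yes/no items to the existing day 1, 2, 3, 4 and 7 surveys, worded identically in both arms and each referring to the time since the last survey: nausea or vomiting; knee giving way; a fall. If a checklist already exists in the monitoring form or case report forms, cite it and confirm that it is used identically in both arms.
- In Section 12, report each item by arm with a risk difference and 95% CI, separately from the any-adverse-event variable and labelled as a descriptive safety outcome.
- Tabulate adverse events by type, so that events possible only with a catheter or pump can be seen apart from those possible in both arms.
- State in Section 12 that non-serious events reported on the telephone calls count towards the adverse-event outcome.

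The cost is three REDCap items and a few lines in Section 12. Surveys become slightly longer and more minor events will be recorded. Sample size and treatment are unchanged.

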12. STATISTICAL ANALYSIS

- *Describe how your data will be used to test the hypotheses.*
- *State clearly what variables will be tested and what statistical tests will be used.*

- *Include sample size calculations.*
- *If this is a pilot study, state which variables will be examined for hypothesis generation in later studies.*

Blinding:

Due to the nature of the intervention (bolus block, continuous infusion pump), it is not possible to blind the physicians or patients.

Consent:

Consent will be obtained during the preoperative visit, prior to surgery.

Randomization:

Subjects will be randomly assigned in a 1:1 ratio to either bolus block or continuous catheter. The randomization will be stratified by hospital (Plainview, Franklin, Huntington, Long Island Jewish, or North Shore University Hospital).

The Biostatistics Unit will develop a randomization procedure using a permuted block design within the Biostatistics Randomization Management System (BRMS).

Additional details of the procedure, including required record keeping, will be further developed upon approval of this protocol. The Biostatistics Unit has extensive experience in implementing and in producing detailed documentation for such procedures.

Intention to Treat (ITT):

All analyses will be carried out according to the ITT principle. The ITT population will be all subjects randomized, regardless of what treatment they actually received. All patients will be analyzed in the group to which they were randomized.

Statistical Considerations:**Specific Aims:**

To compare the efficacy of two postoperative pain control methods (bolus block, continuous catheter) in patients undergoing ACL reconstruction.

Primary Outcome

Outcomes measured on post-operative days 0, 1,2,3,4,7, and at the post-operative follow-up visit. (Outcomes for days 0, 1,2,3,4, and 7 will be obtained via email and electronic surveys . Outcomes for the post-operative follow-up visit will be measured during the postoperative visit which takes place between days 10 and 14. This will be referred to as "Day 10").

- Pain Control

- Maximum pain will be measured on a scale of 0 to 10, where 0 represents no pain and 10 represents the worst possible pain. Patients will report the maximum pain felt in the 24 hours
- Current pain will be measured on a scale of 0 to 10, where 0 represents no pain and 10 represents the worst possible pain.
- Daily opioid consumption (expressed as morphine equivalents).

Secondary Outcomes

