1. Both anesthetists and surgeons recognize the benefits of peripheral nerve catheters (PNCs). The continuous infusion of local anesthetic near a peripheral nerve or plexus produces fewer systemic side-effects than i.v. opioids, increases postoperative patient satisfaction, and can allow for faster functional recovery of the operated limb.
2. Block Failure
 - a. Occasionally, there are instances when the catheter is passed easily but the nerve block fails to provide adequate anesthesia or analgesia.
 - b. This is rare with the use of ultrasound guidance and localization of the continuous catheter.
 - c. In the event of a block failure or inadequate placement that is not providing the patient any relief, the catheter will be removed either by the patient or post operatively depending on when it is discovered.
 - d. The practicing anesthesiologist will discuss with the patient the option of either trying a second time to place the catheter successfully in the post anesthesia recovery area or discontinuing the block altogether.
3. Accidental Catheter Migration/Removal
 - a. The incidence of accidental catheter removal is reported in the literature at about 1%. The use of sterile adhesive tagaderm dressing has been implemented to firmly secure the catheter to the skin to avoid migration or fall out. The dressing is checked to be secure after it has been applied.
 - b. In the event that the catheter is accidentally removed or dislodged during the course of the study, it should be removed and there will be no further intervention once the patient has been discharged home. The patient can place a Band-Aid over the catheter site and notify the coinvestigator or PI.
4. Localized Infection
 - a. Localized inflammation is infrequent (0–10%), and local infection (0–3%), abscess formation (0–0.9%), and sepsis occur even more rarely.
 - b. Transparent dressings are used to reduce the number of dressing changes while appropriately monitoring the site for signs of inflammation
 - c. Since the continuous catheter remains in for 48-72 hours, it does pose a theoretical increased risk of infection compared to a single shot adductor canal block although this has not been proven in the literature. To minimize this risk the site is prepped in sterile fashion with either chlorhexidine or iodine scrub. The injecting physician washes hands and uses sterile gloves and instruments for the course of this procedure.

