18. RESEARCH RELATED HARM/INJURY

- *Describe the availability of medical or psychological resources that subjects might need as a result of anticipated problems that may be known to be associated with the research.*
- *If the research is greater than minimal risk, explain any medical treatments that are available if research-related injury occurs, who will provide it, what will be provided, and who will pay for it.*

Adverse events and planned interventions prior to discontinuation

- Failure of catheter placement despite successful administration of single site injection- any participant who was randomized to receive a continuous

pump, but the catheter was unable to be placed will be discontinued from the continuous pump protocol, however these patient's will continue to be followed according to the above stated protocol and their outcomes assessed in an intent-to treat manner based on their initial randomization.

- Continuous Block failure- if patient perceives no benefit from block but pump appears to be functioning patient will be requested to continue the pumps use until the medication dosing is completed, a perceived block failure will be documented.
- Allergy to local anesthetic- if a patient reports a systemic allergic response including but not limited to shortness of breath, diffuse rash, or angioedema the patient will be recommended to discontinue the intervention and seek emergency care. If the patient reports a local confined rash or skin irritation around the catheter site with no systemic symptoms the patient will be recommended to take a dose of Benadryl and apply a warm compress, if symptoms resolve the patient will remain in the study if there is no resolution the patient will be told to discontinue the medication administration and seek care for further evaluation.
- Persistent pain at catheter site- the patient will be advised to place a cold or warm compress at the catheter site and adjust the adhesive bandage if necessary if these interventions do not alleviate the participants pain within 12 hours the patient will be advised to discontinue the intervention.

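### Sections 16/17 and Section 18 give opposite instructions for a failed catheter block, and handling of block failure is written for one arm only

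*Combined protocol and SAP*

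**What the plan says.** **Sections 16 and 17.** The catheter risk lists (Block Failure, items c and d) say that when the block fails or the placement is inadequate and brings no relief, "the catheter will be removed either by the patient or post operatively depending on when it is discovered". The anesthesiologist then discusses with the patient "the option of either trying a second time to place the catheter successfully in the post anesthesia recovery area" or giving up the block. Failure is described this way: "This is rare with the use of ultrasound guidance and localization of the continuous catheter". No rate is given.

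**Section 18, Continuous Block failure.** If the patient feels no benefit but the pump seems to work, the "patient will be requested to continue the pumps use until the medication dosing is completed", and a perceived failure is documented.

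**Section 18, failure of catheter placement.** A participant randomized to the pump "but the catheter was unable to be placed will be discontinued from the continuous pump protocol". Follow-up continues and the outcome is assessed by intention to treat. A second attempt is not mentioned.

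**Single-shot arm.** Section 16 states, without limiting it to an arm, "Adverse events include but are not limited to block failure". The single-shot risk lists in Sections 16 and 17 cover nerve injury, systemic toxicity and infection. They have no block-failure item.

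**Analysis (Section 12).** The trial is unblinded. The primary outcomes are maximum pain, current pain and daily opioid use from day 0. "All patients will be analyzed in the group to which they were randomized".

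**The concern.** A patient at home whose catheter brings no relief is covered by two instructions that cannot both be followed: take the catheter out, or keep the pump running. The same holds for staff in the recovery area. Section 5 promises identical standardized instructions at every facility, but with this text five hospitals could act differently and each could point to a section that supports it.

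The choice affects what catheter-arm patients actually receive in the first days, which is when the infusion is expected to work and when pain and opioid use are primary outcomes. Intention to treat keeps each patient in the assigned arm. It does not make the handling of failures equal between arms or between sites.

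If Sections 16 and 17 are followed and a failed single-shot block is not repeated, the early contrast includes a repair step in one arm. The planned outputs would not show this. Section 12 reduces adverse events to any or none per subject. The case report form page described in Section 16 is triggered by discontinuation or withdrawal, and a successful second placement is neither.

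**Working it through.** **1. The passages side by side.**

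| Event | Sections 16/17 | Section 18 |
|---|---|---|
| Catheter in place, no relief | Remove; then second placement in recovery, or stop | If the pump works, continue to end of dosing |
| Catheter cannot be inserted | Not clearly covered | Off the pump protocol; second attempt not mentioned |
| Single-shot block fails | No handling stated | No handling stated |

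The first row is a direct contradiction. One could try to separate a confirmed failure (Sections 16/17) from a perceived one (Section 18). But Sections 16/17 define failure by lack of relief and allow the patient to remove the catheter, so at home the two descriptions fit the same patient. The second row is only an ambiguity: Section 18 may describe the situation after a second attempt.

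**2. The plan's own figure.** Section 12 inputs: difference 2, SD 2.5, two-sided alpha 0.01, power 80%.

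- Normal approximation: n = 2 × (2.576 + 0.842)² × (2.5/2)² = 36.5, so 37 per arm.
- Noncentral t: 38.19, so 39 per arm, with 81.0% power at 39.

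The stated 39 per arm reproduces and is not affected by this point.

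**3. Possible shift on one early day.** Shift = f × d × r, where f is the failure rate, d the extra pain points after an unrepaired failure, and r the share of catheter failures repaired. The documents give none of these, so all are assumptions. The worst case is r = 1 in the catheter arm and 0 in the single-shot arm. The standard error of a daily difference is 2.5 × √(2/39) = 0.566. The last column is the rejection rate of a single-day test at nominal 0.01 when there is otherwise no difference between arms (normal approximation).

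| f | d | Shift (points) | Share of 2 points | Expected failures in 39 | Rejection rate |
|---|---|---|---|---|---|
| 1% | 2 | 0.02 | 1% | 0.4 | 0.010 |
| 5% | 2 | 0.10 | 5% | 2.0 | 0.011 |
| 5% | 4 | 0.20 | 10% | 2.0 | 0.015 |
| 10% | 2 | 0.20 | 10% | 3.9 | 0.015 |
| 10% | 4 | 0.40 | 20% | 3.9 | 0.031 |
| 20% | 4 | 0.80 | 40% | 7.8 | 0.12 |

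The last row is hard to square with failure being rare. A shift confined to one of the seven time points in Section 12 averages, over all seven, to between 0.02/7 = 0.003 and 0.40/7 = 0.06 points for f of 1–10%.

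**4. The opposite direction.** A catheter-arm patient left without an infusion, by removal or by discontinuation under Section 18, lowers the observed difference by about 2/39 = 0.05 points, if that patient loses the whole assumed 2-point benefit. Two such patients lower it by 0.10.

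**5. If Section 18 governs and means no second attempt,** no repair is described in either arm and the shift in step 3 is zero.

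**The case against.** A reader might infer that failed blocks are repaired only in the catheter arm and that early results are therefore tilted toward the catheter. The documents do not support that reading.

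- They are silent on repeating a single-shot block; they do not forbid it. Section 11 leaves anesthesia to the anesthesiologist's discretion, and the risk lists are not treatment algorithms.
- The second placement is optional, is offered only in the recovery area, and may end in stopping the block.
- Removal and discontinuation take the infusion away, which works against the catheter, so the net direction is not known.
- Re-placing a catheter can be seen as delivering the assigned treatment rather than as a co-intervention.
- If failure is rare, as stated, the effect is small.

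All of this stands, and it limits any claim of bias to a conditional one.

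It is also fair that recording is partly covered. Block failure is an adverse event in both arms, events are asked about at each visit and call, perceived continuous block failure is documented, and non-receipt of the assigned treatment is noted. What clearly lacks a field is a second attempt, and no count of failures by arm is planned.

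None of these arguments removes the conflict between taking the catheter out and continuing the pump.

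**Conclusion.** The plan contradicts itself on a catheter block that fails while the pump works. It is unclear on whether a second attempt precedes discontinuation when a catheter cannot be inserted. It lists block failure for the whole trial but states its handling for one arm. The missing single-shot rule would, on its own, be no more than missing detail; the opposite instructions are what make this worth correcting.

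The effect on the results cannot be computed from the documents. Under the assumptions shown (failure 1–10%, cost 2–4 points, every catheter failure and no single-shot failure repaired) it is at most about 0.02–0.40 points on a day, or 1–20% of the 2-point design effect. Loss of the infusion pulls the other way. This does not call the sample size or the intention-to-treat analysis into question.

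**What to change.** 1. Reconcile the Block Failure items in Sections 16 and 17 with the two Section 18 items into one consistent rule, including whether a second attempt comes before discontinuation. The choice of rule is for the investigators; none is proposed here.
2. State how block failure is identified and handled in each arm.
3. Record block failure, any second attempt and its time on the case report form in both arms.
4. Report these counts by arm beside the intention-to-treat result.

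The cost is protocol wording and a few case report form fields. The sample size and the planned models stay as they are.
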